**Table 2: Regression Equations for Mediation Analysis**

- A.  $Y = \beta_0 + \tau X_p + \varepsilon$
- B.  $Y = \beta_0 + \tau' X_p + \beta_1 X_1 + \dots + \beta_k X_k + \varepsilon$  for all mediators together  
OR  
 $Y = \beta_0 + \tau' X_p + \beta_i X_i + \varepsilon$  for each mediator separately

## 1 Background

A5333s is an optional mechanistic substudy of REPRIEVE (A5332). Approximately 800 people with HIV (PWH) who are enrolled in REPRIEVE (A5332) were targeted for Mechanistic Substudy of REPRIEVE (A5333s) enrollment.

The overarching aim of the Mechanistic Substudy of REPRIEVE (A5333s) is to better understand the modulation of critical features of coronary plaque morphology with statin therapy, including the progression of noncalcified coronary atherosclerotic plaque (NCP) volume in HIV and the biological factors mediating these effects during statin treatment in HIV. The Substudy will determine potential statin effects to halt progression of non-calcified atherosclerotic plaque and to stabilize morphologic features of plaque vulnerability. Moreover, the study will identify biological factors mediating these changes – be it lipid parameters, such as LDL cholesterol, or markers of inflammation and immune activation. Finally, the study will evaluate whether presence and morphology of subclinical atherosclerotic plaque at baseline relates to CVD events independently of traditional CVD risk factors and markers of HIV-specific immune activation.

This is the Primary Statistical Analysis Plan for the Mechanistic Substudy of REPRIEVE. It expands on details of the statistical analysis plan that were defined in Appendix II of the REPRIEVE (A5332) protocol document. Major changes from the details defined in the protocol are outlined in the version history table below. An overview of the Substudy design is provided below; details of the substudy sample size considerations are in Appendix I, copied verbatim from the protocol.

In preparation for public release of the document with publication of the data, preliminary substudy data and published work from other groups that were used as sample tables have been redacted.

## Version History

Version	Changes Made	Date Finalized
(Protocol)	Original Version (Version 2.0)	Dec 19, 2014
1.0	Clarification that primary outcomes are related to noncalcified plaque; additional secondary plaque outcomes added. HIV-1 RNA and CD4 moved from secondary outcomes to risk factors. HgA1C removed throughout (no longer being tested).	Mar 20, 2023
1.1	For Published release of the SAP ... Section 7: Sample tables of published work from other groups redacted. Appendix II: Draft consort based on early preliminary data removed.	October 4, 2023

## 1.1 A5333S Design Overview

Enrollment into A5333s occurred concurrently with enrollment and randomization into REPRIEVE (A5332) at select US ACTG sites participating in REPRIEVE (A5332). To ensure balance in treatment assignment in the Substudy, randomization in REPRIEVE (A5332) was stratified by anticipated Substudy participation.

Substudy participants were followed for 2 years with serial coronary computed tomography angiography (CCTA) performed at study entry and 2 years. Fasting blood samples for assessment of lipids and select soluble biomarkers were drawn at entry, month 4, and year 2; PBMCs for assessment of cellular markers of immune function were drawn at entry and year 2. The Substudy also included a 2-year assessment of REAP (diet and physical activity) and DASI (physical function), as well as quality of life assessment using the SF-36 at entry and year 2.

Entry blood draws and CCTA were scheduled to occur within 14 days after randomization and prior to the start of randomized treatment. Month 4 evaluations were to be performed  $\pm$  21 days and year 2 evaluations were to be performed  $\pm$  28 days. In light of scheduling concerns and to maximize the collection of follow-up CT scans, the window for year 2 data collection was extended to up to 30 months after the entry CT.

## 1.2 A5333S Hypotheses

### 1.2.1 Primary Hypothesis

Statin therapy will reduce progression of noncalcified coronary atherosclerotic plaque (NCP) volume over two years as measured by CCTA, as compared with placebo in HIV-infected persons at low to moderate traditional ASCVD risk.

### 1.2.2 Secondary Hypotheses

- Decreases in LDL cholesterol levels associated with statin therapy will predict improvement in NCP burden and/or plaque vulnerability features.
- Statin therapy will reduce indices of general inflammation, coagulation, monocyte activation, and arterial inflammation.
- Statin therapy will reduce levels of pro-inflammatory monocyte populations.
- Statin therapy will reduce levels of T-cell activation and exhaustion.
- Changes in levels of immune activation and inflammatory markers will be associated with changes in morphology and composition of NCP.
- Statin therapy will not have a clinically significant effect on glucose and insulin resistance.

## 1.3 A5333S Timeline

- The Substudy opened to enrollment on April 14, 2015; first enrollment occurred on May 6, 2015.
- Substudy enrollment closed on February 6, 2018.
- A memo was sent to Substudy sites on March 12, 2020, requesting completion of all follow-up CT scans by June 1, 2020. The Substudy did not formally close to follow-up at this time, pending a possible extension and additional follow-up CT scan.

## 2 Objectives and Estimands

### 2.1 Primary Objective

To determine the effects of pitavastatin on the morphology and composition of coronary atherosclerotic plaque, (including the progression of noncalcified plaque (NCP) volume), and whether these effects are modulated by markers of inflammation and immune activation.

Primary Estimand	
Estimand description	An estimand defines the target of estimation for a particular trial objective (i.e. “what is to be estimated”). This combines all the estimand elements outlined below into a single, succinct sentence.
Treatment	Treatment groups
Pitavastatin 4mg per day	Pitavastatin 4mg per day or placebo
Target population	Analysis set
PWH on stable ART with low to moderate cardiovascular risk and no known current indication for statin treatment.	All randomized participants with a REPRIEVE (A5332) entry visit. Participants who were consented but never returned to the clinic for their REPRIEVE (A5332) entry visit (regardless of whether the participant was formally randomized) will be considered inadvertent enrollments and excluded.
Variable(s)	Outcome measure(s)
Change in noncalcified plaque volume (NCP)  Change in volume of plaque and calcified plaque will be examined as secondary variables.	See Section 3 for more detailed outcome descriptions • Absolute change in NCP volume from entry to year 2. • NCP progression defined as any increase (>0) in NCP volume or incident NCP for those without NCP at entry (based on qualitative read) For sensitivity analyses, • Qualitative assessment of at least one segment with NCP on the 2 year CT. • Quantitative NCP volume at 2 year CT
Handling of intercurrent events	Handling of missing data
Failure to start statin : Included per randomized treatment (treatment policy) Change in statin strategy : Included per randomized treatment (treatment policy) Includes discontinuation or change of statin Evidence of critical stenosis at treatment start : Included per randomized strategy (treatment strategy) Interval stent placement or bypass *: Included per randomized strategy (treatment policy strategy) Death prior to Year 2 scan : Treated as missing data (hypothetical policy)	Missing data due to missed visits or unreadable scans will be assumed missing completely at random and ignored i.e., the primary analysis will be a complete case analysis including participants with pair baseline and year 2 scans. Sensitivity analyses will include multiple imputation for missing data.
Population-level summary measure	Analysis approach
Mean change NCP volume over 2 years	Linear regression (normal errors assumption). In the event of extreme violation of normality, outcomes will be log transformed (giving a percentage change interpretation of the treatment effect). Modeling will adjust for CD4 and sex (stratification factors), and for baseline NCP volume.

\* Stented or bypassed coronary artery segments are not considered on the entry and year 2 scan as part of the read protocol for plaque volume.

### 2.2 Secondary Objectives

- To determine the effects of pitavastatin on the progression of high risk plaque features including low attenuation plaque and positive remodeling.
- To determine the effects of pitavastatin on detailed markers of immune function including, immune activation (%CD14+CD16+ monocytes, sCD163, sCD14, MCP-1 and T-cell markers), inflammation (Lp-PLA2, hsCRP, hs troponin, oxLDL IL-6), coagulation (D-Dimer) and traditional CVD risk indices

including detailed parameters of glucose homeostasis (insulin, glucose and related indices of insulin resistance such as HOMA-IR).

- To determine the relative contributions of baseline and pitavastatin induced changes in HIV-specific immune activation and traditional risk factors, including LDL, on the presence and progression of coronary plaque and high-risk morphological features in HIV.

### 3 Outcome Measures

#### 3.1 Analysis Windows for Evaluations

Evaluations drawn within the windows of evaluation defined below will be included in outcome measures; evaluations outside these windows will be excluded. It is noted that analysis windows for month 24 evaluations were widened from those originally planned to accommodate scheduling complications due to COVID restrictions.

Evaluation	Entry*	Month 4	Year 2 (Month 24)
CT scan	Any date $\leq$ (First dose+14 days)	-	Target date – 6 months (180 days) to Target date + 12 months (360 days) i.e. Month 18 to Month 36
Fasting lipids	Any date $\leq$ First dose	Target date $\pm$ 60 days	
Soluble biomarkers	Any date $\leq$ First dose	Target date $\pm$ 60 days	
Flow cytometry	Any date $\leq$ First dose	-	
Questionnaires	Any date $\leq$ First dose	-	

\* For participants who never start treatment, evaluations  $\leq$  30-days after A5332 entry.  
Target date = A5332 entry date + (Month\*30)

#### 3.2 Primary, Secondary, and Associated Supportive Outcome Measures

The primary variable of interest for the Substudy is the morphology and composition of noncalcified coronary atherosclerotic plaque. The following NCP outcome measures will be described and compared by treatment group. Corresponding outcomes at entry will be described when appropriate. For the primary analysis, a threshold of <350 HU will be used to define non-calcified plaque.

##### 3.2.1 Change NCP volume over 2 years (Primary)

- Continuous outcome:
  - Absolute change: NCP volume at 2 years – NCP volume at entry
  - Percentage change: (NCP volume at 2 years – NCP volume at entry) / NCP volume at entry (Supportive)
- Based on quantitative read whenever available (including for participants with no evidence of NCP based on the corresponding qualitative read).
  - Participants without a quantitative read and no evidence of NCP based on the corresponding qualitative read will be assigned a value of zero for both absolute and percentage change.

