Treatment group comparisons of continuous outcomes will use t-tests with transformation as needed. In the event of non-Normal distributions even after transformation, Wilcoxon rank sum tests will be preferred. With respect to discrete outcomes, Wilcoxon rank sum tests will be used for ordinal outcomes; Chi-squared test will be used otherwise; Fisher's exact test will be preferred in the event of small cell numbers. All testing will be stratified by sex and CD4 cell count per randomization: while the primary analyses will not be further stratified by enrollment in the Mechanistic Substudy of REPRIEVE (A5333s), sensitivity analyses will be performed including this stratification. Additional perspective regarding the interpretation of the data will be provided through extensive use of confidence intervals and graphical displays.

Given the strong plans for participant follow-up as part of the study, it is anticipated that missing data will be minimized. Unless examination of the data suggest otherwise, missing data will be assumed to be ignorable; participants

lost to follow-up before experiencing a prior endpoint will be considered non-informatively censored. For all participants lost to follow-up, cardiovascular risk factors at the time of their final study visit will be described. In addition, a supportive analysis of time to death from any cause or MACE ([outcome measure 9.2.2.3](#)), including data from vital status and endpoint follow-up following premature study discontinuation will be conducted.

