## 7 Analysis Plan

### 7.1 General analysis Considerations

Outcome distributions will be described with median, Q1, Q3, P10, P90, minimum, and maximum and shown graphically. All primary treatment group comparisons will be performed ITT using a 5% type error. For continuous outcomes, inference will be based on differences in means adjusted for baseline and presented with two-sided, 95% confidence intervals.

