#### Table: Primary and secondary plaque outcomes

Among participants with plaque at entry, descriptive statistics for the change and percentage change in NCP volume over 2 years will be provided by treatment group with group comparisons made with linear regression with adjustment for baseline plaque volume and stratified by sex and CD4.

Among those without NCP at entry, the prevalence of incident NCP over 2 years will be compared with stratified chi-squared test.

To assess the mechanistic study population as a whole, the probability of NCP and total plaque progression over two years (see Section 3.2.2) will be compared by treatment group using a stratified chi-squared test.

The statin effect on high risk plaque features (any), including low attenuation and positive remodeling, will be assessed by comparing differences in the 2-year prevalence of high risk plaque morphology features between treatment groups using chi-squared (or Fisher's exact) tests as appropriate; these analyses will be performed overall and by subgroups defined by the presence of NCP at study entry.

*Sample table from Testosterone study, JAMA 2017*

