## Appendix I Sample Size Considerations

[Copied Verbatim from the REPRIEVE A5333S Protocol, Version 5.0, Section 9.2.]

The target sample size for the Mechanistic Substudy of REPRIEVE (A5333s) is 800 participants that will be approximately equally distributed between the study arms.

This sample size was determined to have high power to detect clinically relevant differences between the two study groups both with respect to plaque progression (among those with plaque at study entry) and rates of incident plaque (among those plaque-free at entry). Specifically, the total sample size of 800 subjects will provide 90% power to detect a 6% difference between the study groups in the percent change in NCP volume over 2 years among those with plaque at entry and 90% power to detect 13 percentage point difference in the probability of plaque development over 2 years. These effect sizes translate to a combined estimated 14 percentage point difference in the probability of NCP progression over two years and are based on the following assumptions:

50% of study participants will have evidence of NCP at study entry [Lo 2010]

A SD of 20% for the percent change over 2 years among participants with evidence of plaque at entry

An annual rate of incident plaque development of 12% among participants without plaque at entry

15% of participants entering the substudy will not be evaluable for study entry or 2 year NCP volume.

Together, the effects of statins acting in these two groups (those with and without evidence of NCP at study entry) will provide for a 7% lower prevalence of NCP after 2-years of statin treatment. Expectations for NCP prevalence and progression both as a whole and according to whether NCP was present at study entry are illustrated in the table below. These estimates are based on a simulation that further assumed the following:

Average volume NCP 250mm^3 (SD=200) among participants with NCP at entry.

Average volume NCP 40mm^3 (SD=20) at 2 years among participants without NCP at entry without statin treatment.

Average volume NCP 20mm^3 (SD=20) at 2 years among participants without NCP at entry with statin treatment.

NCP distributions were also assumed to follow a gamma distribution with size and shape parameters determine to provide the desire mean and standard deviations.

Table 9.2-1: Cells constituting the primary targeted group comparisons are shown in bold.

		At study entry			At two 2 years						

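### Supportive percent change in NCP volume divides by entry volume with no lower limit and is compared on means, so a few small plaques can drive it if reading error is material

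*SAP*

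**What the plan says.** SAP 3.2.1 places two continuous measures under the change in NCP volume. Absolute change comes first. The second is "Percentage change: (NCP volume at 2 years – NCP volume at entry) / NCP volume at entry (Supportive"). Both use the quantitative read whenever there is one, "including for participants with no evidence of NCP based on the corresponding qualitative read". A value of zero is assigned only where there is no quantitative read and no visible NCP. No minimum entry volume is set, and there is no rule for a quantitative entry volume at or near zero. SAP 3.3.4 repeats the definition for the 130 HU threshold.

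SAP 7.2 says that, among participants with plaque at entry, the change and "percentage change in NCP volume over 2 years will be provided by treatment group with group comparisons made with linear regression", adjusted for baseline volume and stratified by sex and CD4. SAP 7.1 bases inference for continuous outcomes on differences in means, "presented with two-sided, 95% confidence intervals". It also states: "All primary treatment group comparisons will be performed ITT using a 5% type error".

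Appendix I sizes the continuous comparison on the percent scale: "the total sample size of 800 subjects will provide 90% power to detect a 6% difference between the study groups in the percent change". It assumes "A SD of 20% for the percent change over 2 years among participants with evidence of plaque at entry", and takes entry NCP volume as gamma with mean 250 and SD 200 mm³.

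SAP 2.1 allows log transformation if normality is severely violated. It does so within the primary estimand and gives no numerical trigger.

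**The concern.** A ratio with a small denominator turns a small absolute error into a very large percentage. A mean, and the regression built on it, gives such values full weight. The planning distribution reaches close to zero, and nothing in the SAP limits, trims or down-weights the smallest entry volumes. If volume readings carry an error in mm³ that does not shrink with the plaque, one or two participants can set the arm mean and widen its interval.

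Percent change is supportive, so the substudy's primary conclusion is not at stake. Even so, it is formally compared by arm and is the only continuous scale on which the sample size was justified. Without a rule written in advance, handling extreme values would become a choice made with the data in hand.

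**Working it through.** **1. The plan's power figure.** Evaluable with NCP at entry: 800 × 0.85 × 0.50 = 340, or 170 per arm (Appendix I). Two-sided 5%, SD 20: SE = 20 × √(2/170) = 2.17 points.
- 6 points: 6/2.17 = 2.77, and Φ(2.77 − 1.96) = 79%.
- 7 points (12% vs 5% in Table 9.2-1): 7/2.17 = 3.23, and Φ(3.23 − 1.96) = 90%.

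The stated 90% therefore matches the table's 7 points, not the 6 in the text. At 6 points it would need an SD of about 17.1%, or about 1,100 enrolled. This gap has nothing to do with reading error.

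**2. How near zero entry volumes come.** Gamma shape = (250/200)² = 1.5625; scale = 250/1.5625 = 160 mm³. P(V < 10) = 0.9%, and 340 × 0.0091 ≈ 3 participants. P(V < 20) = 2.6%, and 340 × 0.0259 ≈ 9. With shape below 2, E[1/V²] is infinite, so in theory any absolute error gives percent change an unbounded variance. At this sample size the practical effect depends on the size of the error.

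**3. The planned SD contains no absolute error.** With E[V²] = 250² + 200² = 102,500, purely proportional change gives these SDs for absolute change:
- control: √(102,500 × 0.20² + 0.12² × 200²) = 68 (table: 68);
- statin: √(102,500 × 0.20² + 0.05² × 200²) = 65 (table: 64).

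**4. What an error of s mm³ per scan adds.** To first order, the extra SD of percent change in the control arm is s × √(1 + 1.12²)/V = 1.50s/V. At s = 5 this is 3 points at V = 250, 29 points at V = 26 and 75 points at V = 10.

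**5. Power for the 7-point difference.** The documents give no reading error, so s is an assumption. The simulation used 170 per arm, gamma entry volumes, lognormal true ratios (means 1.12 and 1.05, SD 0.20), independent normal error on both scans, measured entry volume floored at 1 mm³, and regression on arm and measured entry volume. Independent runs agree to within about two points.

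| s (mm³) | Mean regression | Rank test |
|---|---|---|
| 0 | 90% | 91% |
| 2 | 84% | 89% |
| 5 | 58% | 85% |
| 10 | 23% | 75% |

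At s = 1 the SD stays at 20% and power by mean regression is about 89%. The smallest 5% of entry volumes (17 people) carry 5% of the sum of squares at s = 0, 13% at 2, 42% at 5 and 90% at 10.

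**6. Sensitivity to the lower end.** If all entry volumes exceed 26 mm³ (the table's 5th percentile for control), mean regression keeps about 89% at s = 2 and 88% at s = 5, but 65% at s = 10. The floor applied to measured volume also matters: at s = 5 and 10, power is 53% and 19% with a 0.5 mm³ floor, and 75% and 46% with a 5 mm³ floor.

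**7. The primary outcome.** Absolute change from the table: 30 − 12 = 18 mm³, SD about 66. SE = 66 × √(2/170) = 7.16; 18/7.16 = 2.51; power 71%. In simulation it stays at about 70–74% for s from 0 to 10.

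**The case against.** The strongest reply is that percent change is only supportive. The estimand in SAP 2.1 is mean change in mm³, the other primary outcome is binary progression, and absolute change hardly moves under reading error. That stands, and it limits the point to a supportive analysis.

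The size of the effect also rests on a reading error that the documents do not give, and on the extreme lower tail of a gamma chosen for planning. That stands too. A reader might infer that the planned SD and power hold only with no absolute error at all, or that small plaques are bound to dominate. The documents do not support either. At 1 mm³ the loss is negligible, and the stated 90% for 6 points already fails with no error.

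The log fallback is a partial answer. SAP 2.1 says that it gives a percentage-change interpretation, which can be read as modelling log volumes, so negative percent changes do not rule it out. A log-ratio analysis keeps about 75% power at 5 mm³ and 49% at 10 mm³, better than mean regression but below the rank test. It has no trigger and is written for the primary estimand.

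SAP 7.2 contrasts participants with plaque at entry against those without NCP, so NCP is probably what plaque means there; the wording only needs tightening. SAP 7.1 already requires medians, percentiles and extremes, which would expose an outlier-driven mean but would not change the comparison. Protocol 9.6.1 says "In the event of non-Normal distributions even after transformation, Wilcoxon rank sum tests will be preferred", but that section governs the main trial. It is a precedent, not a rule for the substudy.

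**Conclusion.** The point holds for the supportive percent-change outcome only. Dividing by an unrestricted entry volume and comparing means leaves the result open to a few small plaques once absolute reading error is material. Under the plan's own distribution and a 7-point difference, power by mean regression falls from about 90% to 58% at 5 mm³ and 23% at 10 mm³, while a rank test keeps about 85% and 75%.

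This rests on assumed errors, on independent errors of constant size across volumes, and on the gamma's lower tail. If the true error is about 1 mm³, or up to about 5 mm³ with entry volumes above 26 mm³, little is lost. A reader might infer that the substudy's main finding is at risk; it is not, because absolute change keeps about 70–74% power throughout. The mismatch between 6 points and 90% power is a separate correction and needs no assumption about error.

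**What to change.** In SAP 3.2.1, 7.2 and 3.3.4:

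- Limit percent change to participants with NCP on the entry qualitative read.
- Report medians by arm.
- Compare arms by a Wilcoxon test stratified by sex and CD4.
- If a mean relative effect is wanted, divide the adjusted mean difference in mm³ by the placebo mean entry volume.

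Separately, alongside Appendix I (copied from the protocol), restate the power: about 90% for 7 points, or about 79% for 6 points with SD 20% and 170 per arm.

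The cost is SAP wording, with no new data. The rank test gives up at most about 2 points of power if error is purely proportional. It also tests a shift in distribution and does not supply the baseline-adjusted mean difference, which remains available from the absolute-change analysis.
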